10.1 General Considerations

Safety parameters will be evaluated for the safety dataset.

10.2 Adverse Events

Adverse events will be coded using MedDRA version 17.1 or later.

For adverse events, missing values will be treated as missing, except for causality, intensity, seriousness, and outcome of adverse events. A worst-case approach will be used: if causality is missing, the adverse event will be regarded as related to the IMP; if the intensity of an adverse event is missing, the adverse event will be regarded as severe; if seriousness is missing, the adverse event will be regarded as serious; if onset date is missing, it will be assumed to be the first day of dosing; if outcome is missing, and no date of outcome is present, the outcome is regarded as 'Not Recovered'.

An adverse event with the causal relationship to IMP judged as 'No reasonable possibility' is categorized as unrelated to IMP. An adverse event with the causal relationship to IMP judged as a 'reasonable possibility' is categorized as related to IMP and as an adverse drug reaction.

Treatment-emergent adverse events will be presented in summary tables and listings. The definition of a treatment-emergent adverse event is provided in Section 10.2.1.

10.2.1 Overview of Treatment-Emergent Adverse Events

Adverse events will be regarded as 'pre-treatment' if they occur between screening and the initial injections with IMP. Adverse events which occur in the time interval from initial dosing to 3 months after (1 month=28 days) last dosing of IMP will be considered to be 'treatment-emergent'. Adverse events will be regarded as 'post-treatment' if they occur 3 months (1 month=28 days) or more after the last dosing of IMP.

An adverse event overview summary table will be prepared including the number of patients reporting an adverse event, the percentage of patients (%) with an adverse event, and the number of events (E) reported, for the following categories:

- Treatment-emergent adverse events
- Deaths
- Serious adverse events
- Adverse events leading to withdrawal
- Severe and life threatening adverse events
- Adverse drug reactions

TLF Table: Overall summary of treatment-emergent adverse events – Safety

10.2.2 Incidence of Adverse Events

Treatment-emergent adverse events will be summarized in a table by MedDRA SOC and Preferred Term (PT). The Table will display the total number of patients reporting an adverse event, the percentage of patients (%) with an adverse event, and the number of events (E) reported. Adverse events will be presented by SOC sorted alphabetically and PT sorted in decreasing frequency of occurrence.

For each treatment the following counts are done:

- For number of patients experiencing a particular event, counting will be done by patient and not by event. This is valid for both SOC and PT, i.e., a patient will only be counted once in each SOC and once within each PT.
- For total number of events, counting will be done by event. This is valid for both SOC and PT, i.e., an event occurring more than once for the same patient will be counted for each occurrence.

Summary tables will be prepared for:

- All adverse events
- Adverse events with an incidence $[\geq 5\%]$ of patients in any treatment group
- Adverse events by causality (related/unrelated)
- Adverse events leading to death
- Adverse events by intensity
- Serious adverse events
- Adverse events leading to withdrawal

Supporting data listings will be provided for:

- All adverse events sorted by center and patient no.
- All adverse events sorted by MedDRA PT
- Serious adverse events
- Adverse events leading to death
- Adverse events leading to withdrawal.

In addition, tables summarizing all the treatment-emergent adverse events by MedDRA SOC and PT displaying the total number of patients reporting an adverse event, the percentage of patients (%) with an adverse event, and the number of events (E) reported will be provided.

TLF Table: Incidence of all adverse events by MedDRA System Organ Class and Preferred Term – Safety Analysis Set

TLF Table: Incidence of treatment-emergent non-serious adverse events (>5% cut-off) by MedDRA System Organ Class and Preferred Term – Safety Analysis Set

TLF Table: Incidence of all adverse events by causality, MedDRA System Organ Class and Preferred Term – Safety Analysis Set

TLF Table: Incidence of adverse events leading to death by MedDRA System Organ Class and Preferred Term – Safety Analysis Set

TLF Table: Incidence of all adverse events by intensity, MedDRA System Organ Class and Preferred Term – Safety Analysis Set

TLF Table: Incidence of serious adverse events by MedDRA System Organ Class and Preferred Term – Safety Analysis Set

TLF Table: Incidence of adverse events leading to withdrawal by MedDRA System Organ Class and Preferred Term – Safety Analysis Set

TLF Table: Incidence of treatment-emergent adverse events by MedDRA System Organ Class and Preferred Term – Safety Analysis Set

TLF Table: Incidence of treatment-emergent adverse drug reactions by MedDRA System Organ Class and Preferred Term - Safety Analysis Set

TLF Table: Incidence of treatment-emergent adverse events leading to discontinuations by MedDRA System Organ Class and Preferred Term - Safety Analysis Set

TLF Table: Incidence of treatment-emergent serious adverse events by MedDRA System Organ Class and Preferred Term – Safety Analysis Set

TLF Listing: Listings of all adverse events sorted by center and patient no.

TLF Listing: Listings of all adverse events sorted by MedDRA Preferred Term

TLF Listing: Listings of all serious adverse events

TLF Listing: Listings of all adverse events leading to death

TLF Listing: Listings of all adverse events leading to withdrawal

10.3 Safety Laboratory Variables

Baseline for all laboratory analyses will be the values obtained at the last assessment prior to the first dose of the IMP. Treatment-emergent laboratory data will include tests completed after the first dose of IMP through the residual time of drug effect. End of trial will include the last post-baseline observation during the trial.

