A patient who prematurely discontinues treatment with IMP, or receives prohibited medication (Section 4.3.2), should be called in for an end-of-treatment visit (Section 6.5) as soon as possible (within 30 days) after a decision of treatment discontinuation has been taken. The reason for premature IMP discontinuation should be recorded in the eCRF. The patient should then be contacted by telephone each month throughout the trial period for collection of follow-up information on hospitalizations and potential CV events, and concomitant medication. At the telephone follow-ups, information will be collected using the standardized questions regarding hospitalizations and/or ER visits that may have occurred since the last telephone follow-up as described in Section 8.2.3. In case the patient has experienced a potential CV event, related event documentation will need to be collected for evaluation by the CEC Committee. After 336 days of participation in the trial, the patient should be called in for an end-of-trial visit (Section 6.6).

In case a patient is lost to follow-up, despite every attempt (e.g., certified mail, telephone contact of patient or patient relatives) to get in contact, the vital and medical status of the patient should be investigated an additional last time at the end of the trial for that patient (i.e. 12 months after Visit 1), by accessing the patient's hospital records, or publicly available sources such as national registries, newspaper obituaries and social networking websites. Attempts may also be made to contact the patient or his relatives to ascertain this information. However, the patients have the right to withdraw their consent for collection of this information at any time, without the need to justify their decision.a

In case the patient has withdrawn his consent for participation in the trial, including any follow-up activities, no new data can be entered into the eCRF and data are recorded in the medical records only. Correction of previous data entries and/or entering of data related to visits/procedures done prior to but made available after withdrawal of consent (e.g. laboratory results) will be allowed unless the patient disapproves it.

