## 6.6 End-of-Trial Visit / Visit 14 (Month 12)

Patients should be called in for an end-of-trial visit after 336 days of participation in the trial.

The following must take place at the End-of-Trial visit:

- IPSS
- PRO (DASI, CAQ and EQ-5D-5L)
- Health economics (CV-related hospitalization events, CABG/PCI procedures and ER visit events)
- 12-lead ECG
- Vital signs (pulse and blood pressure)
- Blood collection for central laboratory analysis of:
  - Testosterone (*Note: Not in patients who have discontinued treatment with IMP and have performed an end-of-treatment visit.*)
  - PSA (*Note: Not in patients who have discontinued treatment with IMP and have performed an end-of-treatment visit.*)
  - Clinical chemistry and hematology parameters
  - Glycemic and metabolic parameters (*Note: The blood samples must be taken while the patient is in fasting state, i.e. minimum of 8 hours without caloric intake.*)

- Urinalysis (dipstick)
- Body weight, waist and hip circumference

- Physical examination
- Radiographic imaging (bone scan). (Imaging can be performed up to 7 days before the End-of-Trial visit.)
- Drug accountability
- Recording of any change in use of concomitant medication
- Recording of adverse events, including CV-related signs
- Completion of End-of-Trial form

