The proportion of patients castrated at day 28, 168 and 336 will be presented by treatment group, along with the number of patients with testosterone measurements at each assessment. Castration is defined as testosterone levels ≤ 0.5 ng/mL. Further, the proportion of patients castrated at both day 28 and 168, as well as at all three visits will be presented along with the number of patients with assessments at each of the corresponding times. For patients discontinuing treatment during the trial, any testosterone data collected after the date of discontinuation will be excluded from the analysis.

TLF Table: Secondary Endpoint: Probability of testosterone levels remaining at castrate levels – FAS

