10.3.1 Summary Statistics

Mean change and mean percentage (%) change from baseline to the end of trial will be presented for each laboratory variable. In addition, descriptive statistics, i.e., the number of patients with data,

Page 38 of 51

mean (standard deviation), median, minimum, and maximum values, will be presented for observed values and change from baseline at each time-point for each laboratory variable.

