10.4.1.1 Summary Statistics

Mean change and mean percentage (%) change from baseline at end of trial will be presented for each vital signs variable. In addition, descriptive statistics, i.e., the number of patients with data, mean (standard deviation), median, minimum, and maximum values, will be presented for observed values and change from baseline at each time-point for each vital signs variable.

TLF Table: Summary of vital signs parameters by visit – Safety Analysis Set

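### SAP 10.3 and 10.4.1 do not limit the end-of-trial safety value to on-treatment data, so early stoppers who return at Day 336 enter the descriptive change tables with an off-drug value

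*SAP*

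**What the plan says.** SAP 10.3 (laboratory) and 10.4.1 (vital signs) each give two definitions in succession. The first sets a treatment-emergent period; for laboratory data it reads "Treatment-emergent laboratory data will include tests completed after the first dose of IMP through the residual time of drug effect". The second defines the end-of-trial value: "End of trial will include the last post-baseline observation during the trial". The limit in the first definition is not carried into the second, and neither section gives the residual period in days.

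The end-of-trial value feeds the summary tables. For laboratory data (SAP 10.3.1): "Mean change and mean percentage (%) change from baseline to the end of trial will be presented for each laboratory variable". For vital signs (SAP 10.4.1.1): "Mean change and mean percentage (%) change from baseline at end of trial will be presented for each" variable. Safety tables use the safety set, which SAP 6.3 analyses by treatment actually received.

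For a patient who stops study drug or receives prohibited hormonal therapy, Protocol 4.4 requires an End-of-Treatment visit, then monthly telephone contact, and then: "After 336 days of participation in the trial, the patient should be called in for an end-of-trial visit". Protocol 6.6 lists vital signs, urinalysis, glycemic and metabolic samples, and "Clinical chemistry and hematology parameters" at that visit. Only testosterone and PSA are waived for patients who have stopped (also Protocol Table 1, footnote m).

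For testosterone, SAP 9.3.7 states that in patients who discontinue, "any testosterone data collected after the date of discontinuation will be excluded from the analysis".

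**The concern.** An early stopper who attends Day 336 has two candidate values: one from the End-of-Treatment visit, close to his last exposure, and one from Day 336. The SAP wording selects the second. It may have been taken many months after the last dose, or on another ADT. Switching is foreseeable: inclusion criterion 4 selects men for whom at least 12 months of ADT is intended, Protocol 3.5.8 leaves treatment after discontinuation to normal practice, and SAP section 4 asks for special attention to patients who stop study drug and start an alternative.

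The value is then tabulated under the study drug received. Elsewhere the SAP separates on-drug from off-drug information: testosterone after discontinuation is excluded, time-to-event endpoints are censored at discontinuation or prohibited hormonal therapy (9.1), and adverse events stop being treatment-emergent 3 × 28 = 84 days after the last dose (10.2.1). The change-from-baseline tables have no such separation, although change in vital signs is a named safety endpoint. At stake is whether the tabulated mean change in each arm describes the drug named in the column heading.

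**Working it through.** The plan states no figure on this point, so there is none to reproduce. The check is date arithmetic on the visit schedule, followed by an illustration of size.

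**Step 1. Time since last dose at Day 336.** Inputs: dosing days from Protocol Table 2 (degarelix every 28 days, Day 0 to 308; leuprolide Days 0, 84, 168 and 252) and the 84-day adverse-event limit in SAP 10.2.1. Formula: 336 − day of last dose.

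| Last dose | Degarelix | Leuprolide |
|---|---|---|
| Day 308 | 28 days (completer) | – |
| Day 280 | 56 | – |
| Day 252 | 84 | 84 (completer) |
| Day 224 | 112 | – |
| Day 168 | 168 | 168 |
| Day 84 | 252 | 252 |
| Day 56 | 280 | – |
| Day 0 | 336 | 336 |

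A degarelix patient last dosed on Day 56 supplies a value 280 days after that dose, 280 − 84 = 196 days beyond the adverse-event limit. A degarelix patient last dosed on Day 280 is still inside that limit.

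**Step 2. Which tables use the rule.**
- Mean and mean percentage change to end of trial, laboratory and vital signs (SAP 10.3.1, 10.4.1.1): yes.
- Hematology and chemistry shift tables (SAP 10.3.2): no; they take the worst in-treatment value.
- Markedly abnormal vital signs (SAP 10.4.1.2): no; they take treatment-emergent values.
- Summaries by time-point (SAP 10.3.1, 10.4.1.1): they do not use the rule. They carry no stated on-treatment limit either, so stoppers' Day 336 values can also sit in the Visit 14 row.

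**Step 3. Illustrative size.** Let D be the on-drug mean change, s the share of patients who are early stoppers with a Day 336 value, and r the fraction of the change reversed by then. Both s and r are assumptions.

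Tabulated change = (1 − s)D + s(1 − r)D = D(1 − s·r).

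| s | r = 0.5 | r = 1 |
|---|---|---|
| 5% | 97.5% of D | 95% |
| 10% | 95% | 90% |
| 20% | 90% | 80% |
| 30% | 85% | 70% |

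If both arms have the same true change but different stopping shares, say 5% and 20%, the rule alone produces an arm difference of (0.20 − 0.05)·r·D = 0.15·r·D, which is 7.5% of D at r = 0.5 and 15% at r = 1.

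**Step 4. Would an 84-day cut-off work?** A leuprolide completer is nominally 336 − 252 = 84 days from his last dose at Visit 14. With ±7 days on both the dose and the visit, the permitted gap is 84 ± 14, or 70 to 98 days. A degarelix completer is at 28 ± 14, or 14 to 42 days. A strict 84-day cut would therefore remove some fully treated patients, and only from the leuprolide arm.

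**The case against.** The strongest case is that the SAP does what the protocol asks. Protocol 9.8.3 and 9.8.4.3 already specify change from baseline at End-of-Trial, and Protocol 6.6 deliberately collects safety samples from stoppers at Day 336. A summary labelled end of trial that uses end-of-trial data is labelled accurately, and preferring an on-drug summary is partly a choice of estimand. This stands to the extent that the off-drug value does not come from the SAP wording alone. It does not explain why the SAP defines a treatment-emergent period in one sentence and leaves it out of the next, or why the tables do not mark which values are off drug.

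It is also fair that testosterone is not a full parallel. It monitors castration by the study drug, and its Day 336 sample is not scheduled in stoppers who have had an End-of-Treatment visit. It shows that the SAP recognises the issue, not that safety data must follow the same rule.

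Further points limit the reach, and they stand. No test is planned on these tables. On-drug vital signs remain visible month by month in the by-visit summary. Stoppers who withdraw or are lost contribute an earlier value, often from the End-of-Treatment visit.

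A reader might infer that fasting glucose, insulin and lipids are the main casualty, since they have no scheduled sample between Visit 2 and the End-of-Treatment or End-of-Trial visit. The documents do not settle this. Protocol 7.3.9 describes safety laboratory variables as chemistry and hematology and lists glycemic and metabolic evaluations separately, and parts of the exploratory sections are redacted.

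**Conclusion.** The point holds for the descriptive tables of mean and mean percentage change to end of trial, for laboratory variables and vital signs, and for early stoppers who attend Day 336. For them the End-of-Treatment value is replaced by one taken off study drug or on another ADT.

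The size cannot be fixed. The documents do not give the share who stop study drug yet return at Day 336. The 5% drop-out in SAP 3.2.1 and Table 1 is a different quantity. The range of 97.5 to 70% of the on-drug change rests on assumed shares of 5 to 30% and assumed reversal of half to all.

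Two stronger readings are not supported. A reader might infer that the safety results as a whole are diluted; the shift tables and the markedly abnormal vital-sign table are outside the rule. A reader might also infer a known direction of bias. Men who move to another ADT need not show reversal, and full reversal and a switch of drug class describe different patients, so one dilution figure cannot cover both.

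**What to change.** In SAP 10.3 and 10.4.1, base the mean and mean percentage change on the last on-treatment value:
- patients who complete study drug: the Visit 14 value;
- early stoppers, including those called in because of prohibited hormonal therapy: the last value up to and including the End-of-Treatment visit.

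Show the Day 336 values of early stoppers in a separate row labelled off-treatment, and apply the same separation to the Visit 14 row of the by-time-point summaries. The End-of-Treatment visit may follow the decision to stop by up to 30 days, so it is the nearest scheduled value rather than a strictly on-drug one; a footnote can say so.

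If a residual period in days is stated for the treatment-emergent tables, it needs an allowance for the dosing and visit windows, so that leuprolide completers at 70 to 98 days after their last dose are kept.

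This is a tabulation rule only and changes no visit, sample or treatment. The cost is a revised definition and one extra row per table. The off-treatment row will hold fewer patients than the main row, so its means will be less precise.

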10.3.1 Summary Statistics

Mean change and mean percentage (%) change from baseline to the end of trial will be presented for each laboratory variable. In addition, descriptive statistics, i.e., the number of patients with data,

Page 38 of 51

mean (standard deviation), median, minimum, and maximum values, will be presented for observed values and change from baseline at each time-point for each laboratory variable.

10.3.2 Laboratory Variable Changes Relative to Normal Range

Changes relative to normal ranges are presented with shift tables with total number of patients, and number and percent of patients who experienced a shift by treatment group and period. The following categories for shift tables are defined:

• Low: Values which are below the lower reference range limit;

• Normal: Values which are within the lower and upper reference range;

• High: Values which are above the upper reference range limit.

• Absent: No value for measured variable (for urinalysis only)

• Present: Any value obtained for measured variable (for urinalysis only)

For all hematology and clinical chemistry variables, shift tables will be prepared to compare baseline values to the worst in-treatment value. More specifically, for hematology and clinical chemistry, tables presenting the changes from *Low* or *Normal* to *High* and from *High* or *Normal* to *Low* will be provided. For urinalysis variables, shift tables will summarize the number (%) of patients who had "absent" values at baseline and "present" values during the treatment period.

TLF Table: Incidence of hematology laboratory variable changes relative to normal range – Safety Analysis Set

TLF Table: Incidence of chemistry laboratory variable changes relative to normal range – Safety Analysis Set

TLF Table: Incidence of urinalysis variable changes relative to normal range – Safety Analysis Set

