### **7.3.9 Clinical Laboratory Variables**

Blood samples for clinical laboratory analyses will be collected at the time points indicated in Table 1. The clinical laboratory variables to be evaluated are presented in Table 3. The analyses of clinical laboratory variables will be performed at a central laboratory using appropriate and validated methods.

Urine samples for urinalysis, will be collected at the Screening visit, at Visit 2 (prior to dosing), and at the End-of-Trial visit. The samples will be analyzed using a dipstick test at the clinic.

Blood samples for assessment of safety laboratory variables (clinical chemistry and hematology) will be collected at the Screening visit, at Visit 2 (prior to dosing) and at the End-of-Trial visit. In addition, blood samples for assessment of clinical chemistry will be collected at Visits 3 and 8 to allow for periodic safety monitoring for QT prolongation.

Blood samples for glycemic evaluations will be collected at the Screening visit, at Visit 2 and at the End-of-Trial visit. At the Screening visit, HbA1c (glycosylated hemoglobin) will be tested in all

patients to rule out uncontrolled diabetes ( $HbA_{1c} > 10\%$ ). Fasting plasma glucose and fasting serum insulin are to be measured at Visit 2 and at the End-of-Trial visit.

Blood samples for metabolic evaluations will be collected at Visit 2 and at the End-of-Trial visit.

The patients have to be in fasting state (minimum of 8 hours without caloric intake) prior to blood sampling for glycemic and metabolic evaluations at Visit 2 and at the End-of-Trial visit.

The total amount of blood, including blood samples for exploratory analyses (Section 7.3.10), planned to be collected from each patient during the course of the trial is approximately 200 mL. In case a patient is performing an unscheduled visit, an additional amount of blood might be taken (approximately 20 mL per visit, if applicable).

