#### **9.8.4.3 Safety Laboratory Variables**

Mean change and mean percentage (%) change from baseline to the End-of-Trial will be presented for each laboratory variable.

Incidence of changes in laboratory values relative to normal reference ranges will be summarized.

Incidence of changes in urinalysis will be summarized.

Laboratory results adjudicated by the CEC Committee as MACE components will be listed.

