10.3.4 Urinalysis

Incidence of changes in urinalysis will be summarized by treatment. A summary table with number of patients with change from *Absent* at baseline to *Present* during trial will be summarized.

TLF Table: Incidence of changes from baseline in urinalysis measurements during the trial – Safety Analysis Set

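### SAP 10.3.2 classifies urinalysis by whether a value exists, not by negative or positive result, so taken literally its Absent-to-Present tables come out near empty

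*SAP*

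**What the plan says.** The protocol (7.3.9) has urine tested on site: "The samples will be analyzed using a dipstick test at the clinic". On timing it says: "Urine samples for urinalysis, will be collected at the Screening visit, at Visit 2 (prior to dosing), and at the End-of-Trial visit". The flow chart in Protocol Table 1 adds the End-of-Treatment visit. Protocol Table 3 lists seven urinalysis variables: blood, glucose, ketones, leucocytes, pH, protein and nitrites. For reporting, Protocol 9.8.4.3 promises: "Incidence of changes in urinalysis will be summarized".

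SAP 10.3.2 sets the shift-table categories. Low, Normal and High compare a result with its reference range, and the tables built on them are for hematology and clinical chemistry. Urinalysis has two categories of its own: "Absent: No value for measured variable (for urinalysis only" and "Present: Any value obtained for measured variable (for urinalysis only". For these variables, "shift tables will summarize the number (%) of patients who had 'absent' values at baseline and 'present' values during the treatment period". SAP 10.3.4 repeats the Absent-to-Present count over the trial: "Incidence of changes in urinalysis will be summarized by treatment".

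The baseline rule in SAP 10.3 is: "Baseline for all laboratory analyses will be the values obtained at the last assessment prior to the first dose of the IMP".

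**The concern.** A dipstick that reads negative for blood has still produced a result. Under the stated definitions a result of any kind makes the variable Present, and only the lack of a result makes it Absent. The line is drawn between tested and not tested, whereas the protocol's purpose needs it drawn between negative and positive.

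At stake is what the two urinalysis tables can show. If programmed as written, a row of zeros in both arms could be taken to mean that neither drug was followed by new blood, protein or glucose in urine, when the table could not have registered such a change.

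**Working it through.** The documents state no urinalysis count or rate, so there is no figure to reproduce. The check applies the definitions to each possible pair of results.

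**Inputs.** The two category definitions (SAP 10.3.2); the rule that only Absent to Present counts (SAP 10.3.2 and 10.3.4); baseline as the last pre-dose assessment (SAP 10.3); dipsticks at both Screening and Visit 2 before dosing (Protocol 7.3.9); the screening dipstick result required before randomization (Protocol 6.2, and note g to Protocol Table 1); 545 patients randomized (SAP section 3), used for scale only.

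**Step 1: classify each pair under both readings.**

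| Baseline | Later test | Literal: value = recorded result | Alternative: value = detected amount |
|---|---|---|---|
| Negative | Positive | Present to Present, not counted | Absent to Present, counted |
| Negative | Negative | Present to Present, not counted | Absent to Absent, not counted |
| Negative | Not done | Present to Absent, not counted | Absent to Absent, same as a negative |
| Not done | Negative | Absent to Present, counted | Absent to Absent, not counted |
| Not done | Positive | Absent to Present, counted | Absent to Present, counted as if baseline were negative |
| pH measured | pH measured | Present to Present, not counted | Present to Present, not counted |

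The first row is the change the table exists to show, and the literal reading misses it.

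**Step 2: how many patients could be counted under the literal reading.** Only a patient with no baseline value can shift. Because baseline is the last pre-dose assessment, a missed Visit 2 dipstick falls back to Screening, so both must be missing. For patients handled per protocol that cannot happen, and the expected count is 0 in each arm.

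To allow for departures, suppose a share m is missing at each of the two visits, independently. The documents give no such share; 2% to 5% is an assumption for illustration. The share with no baseline is m × m:

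- m = 2%: 0.02 × 0.02 = 0.0004, and 0.0004 × 545 = 0.2 patients
- m = 5%: 0.05 × 0.05 = 0.0025, and 0.0025 × 545 = 1.4 patients

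These are totals over both arms, before asking whether a later dipstick exists. The requirement for a screening result before randomization pushes them lower; clustering of missed tests in the same patients would push them higher. The tables use the Safety Analysis Set, whose size the documents do not state.

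**Step 3: what the alternative reading leaves open.** New positives are now counted, but three gaps remain. First, there is no category for a test not done and no denominator rule for the percentage. A missing follow-up dipstick would count as no change, and a missing baseline as negative. Second, no dipstick grade separates Absent from Present, so a trace result has no assigned class. Third, pH has a value whenever it is tested, so it stays Present throughout.

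**The case against.** The best answer is that the intended meaning is clear enough. The section concerns changes relative to the normal range, the text speaks of patients who had absent values (which presupposes that a test was done), and for an analyte such as blood or protein the labels naturally mean not detected and detected. A programmer would probably code it that way. This stands as a statement of likely intent, and it means an empty table is not certain. It does not settle the three gaps in Step 3, and an analysis plan should not depend on a programmer departing from its written definition.

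The second answer is that abnormal urine results appear elsewhere. SAP 10.3.3 lists patients with any abnormal laboratory value, and Protocol 7.3.9 makes clinically significant abnormal values adverse events, which are tabulated by arm. This also stands in part. But a listing is not an incidence, and the adverse event route takes only what the investigator judges clinically significant. SAP 10.3.1 gives means and mean changes, which do not give the incidence of new findings, and the markedly abnormal criteria in SAP Appendix 1 cover vital signs and ECG, not laboratory values.

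The third answer is that urinalysis is not an endpoint and these tables carry no test. That is correct and limits the weight of the point.

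A reader might go further and infer that the tables would fill with missing baseline dipsticks presented as new findings. The documents do not support that: with two pre-dose dipsticks, the last-assessment baseline rule and a screening result required before randomization, almost no baseline is missing. The literal failure is a near-empty table, not a falsely full one.

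**Conclusion.** The point holds as a minor defect in a stated rule. Followed literally, both urinalysis tables would show about zero shifts per arm regardless of follow-up results. This assumes that the protocol's screening requirement is met and that a missed Visit 2 dipstick falls back to Screening. Read as not detected versus detected, the tables serve their purpose for six of the seven variables, but still confuse a test not done with a negative one, leave trace unclassified and give nothing useful for pH.

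The damage is confined to descriptive safety output. These are the only planned by-arm incidence summaries of urinalysis changes, so they are worth getting right. It would be wrong to infer that urinary safety findings are lost altogether, since listings and adverse events capture some of them. No primary, secondary or exploratory efficacy analysis is affected.

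**What to change.** In SAP 10.3.2, and by reference in 10.3.4:

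- Define Absent as a recorded negative result.
- Define Present as a recorded positive result at or above a stated dipstick grade, and say how trace is classed.
- Show not done as a separate line, and base the percentage on patients with a recorded result both at baseline and afterwards.
- Take pH out of the Absent/Present tables and present it with the Low, Normal and High categories already defined in 10.3.2, naming the reference range used for the clinic dipstick.

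The cost is a few lines of SAP text and one derivation in the laboratory dataset, using data already collected.
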